### **5.9. Optional Continuation Phase after Eight Cycles of Pembrolizumab**

As described in section 5.1 this pilot study is intended to offer a total of eight doses of pembrolizumab on every three weekly cycles with decitabine given on alternative cycles as initial induction therapy.

In the event that a patient achieves a response of mCR, mCRi, CR, CRi, PR or SD (see Appendix A) at the end of cycle 8 assessment then additional cycles of pembrolizumab and decitabine therapy will be offered. These additional cycles will be given according to the same schedule (see section 5.1) with the below exceptions. Pembrolizumab in cycle 9 (ie: first cycle of continuation phase) may be delayed up to 7 days to allow post-induction phase staging to be completed. No more than 35 cycles (ie: two years) of therapy will be offered. Decitabine 20 mg/m^2 will be given for not more than ten consecutive days every six weeks and may be prescribed and supplied by non-study physician.

### **5.10. Subject Replacement Strategy**

If a patient discontinues treatment prior to receiving fourth dose of Pembrolizumab, due to patient or investigator action/decision, that patient may be replaced with another subject. Maximum accrual will be fifteen subjects.

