**Subjects of Study:**

Number	Sex	Age-range
10	M/F	18-99

(Maximal accrual including replacement subjects: 15)

Ionizing Radiation for Research:	No
Off-Site Project:	No
Multi-center trial:	No
DSMB Involvement:	Yes
Tech Transfer:	Yes
IND:	Yes (IND number 131826)

Version: 11.0

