### 6.5.3. Post-study follow-up stage (all patients)

After the end of treatment, each subject will be followed for 30 days for adverse event monitoring. After a subject completes the study they will be offered the opportunity to consent to an alternative hematology branch protocol (eg: 94-H-0010) to allow follow-up contact, ordinarily by telephone, approximately every 13 weeks to assess for remission and survival status until death, withdrawal of consent, or the end of the study, whichever occurs first.

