### **8.3. Statistical safety monitoring**

Given that the primary hypothesis is for feasibility, we will monitor the progress of the patients in the study. Following Geller *et. al.*, we use a Bayesian stopping rule for safety. For a given patient the safety endpoint is defined as grade 4 or 5 treatment related adverse event (excluding hematological toxicity, see section 9.1.2). This endpoint encompasses causes of death and severe toxicity from pembrolizumab and/or decitabine therapy during the induction phase (eight cycles) and, as such, is a suitable safety endpoint. Before the data are

collected, we assume that the prior distribution of the proportion of patients who will experience the safety endpoint follows a beta distribution. We combine the beta prior and the proportion data to form a beta posterior.

We anticipate the rate of treatment-related toxicities and deaths within the study period to be 50% or less. Since the proportion is a realization of a beta distribution, the proportion parameter is not a fixed quantity but a random variable. We assume the prior mean to be 0.3, and our prior knowledge is “worth” two patients. The conditions are satisfied where we set  $a=0.6$  and  $b=1.4$  for the beta distribution. Note that  $a+b$  is interpreted as the measure of contribution of the prior distribution. The subjective contribution of two patients, added to the sample of ten patients, is quite modest and does not exert undue influence on the data characteristics.

We set the stopping boundary for the event that the posterior probability, given accruing data, exceeds 0.8 when the posterior proportion of the specified events is greater than 0.5. That is,  $\text{Prob}(p>0.5|\text{data})>0.8$ . The resulting boundaries are shown in the Table 8 below.

No. Patients	Stop if toxicities reaches or exceeds	Posterior Probability
3	3	0.86
5	4	0.81
7	5	0.78
8	6	0.86
10	7	0.83

We evaluated the performance of this stopping rule with computer simulations. In each simulation we generated a study with 10 independent Bernoulli trials, each with prior proportion  $p$  for having toxicity and compared the outcome with the stopping boundary. We repeated the simulation 100,000 times and counted the number of times the study was stopped. We did this for a number of different prior proportions to investigate whether our benchmark of 0.5 is appropriate (Table 9 below).

Proportion of SAE= $p$	0.2	0.35	0.5	0.65	0.8

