Proportion of Stopped Studies	1.36%	9.74%	31.77%	64.73%	92.33%
Average number of subjects	9.92	9.49	8.44	6.76	4.83
Average number toxicities	1.99	3.33	4.22	4.39	3.86

These results suggest our stopping rule has a low probability of stopping a study when the proportion of toxicities is below the benchmark value of 50% toxicities is high when above this cut off.

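### Up to 15 patients may be treated, but the stopping boundaries (Table 8) and simulated operating characteristics (Table 9) cover exactly 10

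*Combined protocol and SAP*

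**What the plan says.** The summary page gives 10 subjects and adds "Maximal accrual including replacement subjects: 15". Section 5.10 explains the difference: "If a patient discontinues treatment prior to receiving fourth dose of Pembrolizumab, due to patient or investigator action/decision, that patient may be replaced". It repeats the ceiling: "Maximum accrual will be fifteen subjects". Section 8.2 gives a sample size of 10.

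Section 8.3 uses a Beta(0.6, 1.4) prior and this criterion: "We set the stopping boundary for the event that the posterior probability, given accruing data, exceeds 0.8" that the toxicity proportion is above 0.5. Table 8 lists boundaries of 3/3, 4/5, 5/7, 6/8 and 7/10, and ends there. Table 9 was obtained as follows: "In each simulation we generated a study with 10 independent Bernoulli trials". From it the section concludes that "our stopping rule has a low probability of stopping a study when the proportion of toxicities is below the benchmark value".

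The endpoint is a grade 4 or 5 treatment-related event, haematological toxicity excluded. It is meant to capture death and "severe toxicity from pembrolizumab and/or decitabine therapy during the induction phase (eight cycles"). Section 8.3 does not mention replacement.

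**The concern.** A replacement patient is an additional treated patient. After one replacement the trial may go on to an 11th patient, for whom Table 8 has no row. Someone working from the printed table alone could see 6 toxicities in 10 (no stop), then 5 more in the next 5, and cross no printed line, although 11 of 15 has a posterior probability of 0.941.

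Table 9 has the matching gap. Its stopping probabilities and average numbers of subjects are what an ethics committee or the DSMB would use to judge the rule, and they describe a trial that cannot exceed 10.

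Section 8.3 also leaves one point unsaid. A replaceable patient has had at most three pembrolizumab doses, while the endpoint window is eight cycles. Section 5.8.1 takes a patient off treatment for any grade 4 treatment-emergent event, so a patient who meets the safety endpoint may also leave before the fourth dose. Section 8.3 should say that such a patient remains in the count.

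**Working it through.** **Inputs.** Prior Beta(0.6, 1.4), criterion Prob(p>0.5|data)>0.8, and boundaries 3/3, 4/5, 5/7, 6/8, 7/10 (section 8.3). Planned size 10 (section 8.2). Ceiling 15 (summary page and section 5.10). The documents give no replacement share, so 20% is assumed, with 10% to 30% as the range.

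**Step 1: reproduce Table 8.** After x toxicities in n patients the posterior is Beta(0.6+x, 1.4+n−x). For 7/10 this is Beta(7.6, 4.4), so P(p>0.5)=0.832 (printed 0.83). The other rows give 0.864, 0.814, 0.780 and 0.857, matching the printed 0.86, 0.81, 0.78 and 0.86.

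**Step 2: reproduce Table 9.** An exact recursion over independent patients, stopping at the printed rows with a maximum of 10, gives 1.39/9.71/31.64/64.88/92.27% stopped at p=0.2/0.35/0.5/0.65/0.8. Table 9 states 1.36/9.74/31.77/64.73/92.33%. Mean subjects are 9.92/9.49/8.45/6.76/4.83 (stated 9.92/9.49/8.44/6.76/4.83). Table 9 is therefore a 10-patient calculation.

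**Step 3: extend the boundary under the same criterion.** The smallest counts whose posterior exceeds 0.8 are 8/11 (0.888), 8/12 (0.812), 9/13 (0.869), 10/14 (0.911) and 10/15 (0.853). Which can be reached without an earlier crossing?

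- A trial still running at 10 has at most 6 toxicities, so at most 7 at 11. The row 8/11 cannot trigger.
- At 12 it can have 8, and Beta(8.6, 5.4) gives 0.812. This row can trigger.
- A trial still running at 12 has at most 7, so at most 8 at 13 and 9 at 14. Neither 9/13 nor 10/14 can trigger.
- At 15 it can have 10, and Beta(10.6, 6.4) gives 0.853. This row can trigger.

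Two rows are therefore enough.

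**Step 4: operating characteristics of the permitted design.** Each patient has toxicity with probability p and is replaced with probability r, independently. Everyone treated is counted. The trial ends at a crossing, at 10 non-replaced patients, or at 15 treated. The last line is the upper limit, in which accrual runs to 15 unless the rule stops it.

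| Design | Stop, p=0.2 | p=0.35 | p=0.5 | p=0.65 | p=0.8 | Mean treated, p=0.5 |
|---|---|---|---|---|---|---|
| Table 9, as stated | 1.36% | 9.74% | 31.77% | 64.73% | 92.33% | 8.44 |
| r=20%, rows 8/12 and 10/15 added | 1.4% | 10.1% | 33.8% | 69.1% | 94.6% | 10.1 |
| All 15 places used, same rows | 1.4% | 10.3% | 35.9% | 73.7% | 97.0% | 11.8 |

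For r=10% and 30% the stopping probability is 32.5% and 34.8% at p=0.5, and 66.6% and 71.2% at p=0.65. With r=20% and only the printed rows, it stays at the 10-patient values (31.6% and 64.9%). At r=20% the chance of treating an 11th patient is 61% at p=0.5 and 31% at p=0.65.

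**The case against.** The strongest reply is that the criterion in section 8.3 applies to accruing data with no limit on n, so the boundary after patient 10 is already determined. That stands. The 6/10-then-5/5 sequence would meet the criterion at 8 of 12. A reader might infer that patients 11 to 15 have no stopping rule at all, and the text does not support that. What is missing is the printed boundary and its operating characteristics.

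A reader might also infer that replacement weakens the rule, because early leavers have less exposure and dilute the count. That compares different toxicity rates. If 20% of patients leave with no toxicity and the rest have a rate of 0.65, the rate over all treated patients is 0.8×0.65=0.52. At 0.52 the 10-patient rule with no replacement stops in only 35.7% of trials. The fall from 64.9% reflects a less toxic treated group. At an equal overall rate, with the criterion extended, stopping becomes slightly more likely.

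A third inference is that replaced patients drop out of the safety count, or that the choice of denominator decides the outcome, as 7/10 stops (0.832) and 7/12 does not (0.630). No section removes a treated patient from the count. Section 6.5.3 says "After the end of treatment, each subject will be followed for 30 days for adverse event monitoring", and Table 7 includes all patients in the feasibility summary, although that does not define the stopping denominator. A trial at 7/10 has already stopped and never reaches 7/12 by that route. Section 8.3 should still state the counting rule, but its silence is missing detail and not a stated exclusion.

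Finally, 15 is a ceiling that needs five replacements, replacement is optional, and section 11.3 says accrual closed on November 30, 2017. All of this stands and limits the weight of the point.

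**Conclusion.** The point holds and is minor. The printed boundaries and the stated operating characteristics belong to a 10-patient trial, while the protocol permits 15. With one toxicity rate for all patients, everyone counted and the criterion extended, the stopping probability rises by about 2 points at p=0.5 and 4 points at p=0.65 for an assumed 20% replacement. If all 15 places are used, it rises by about 4 and 9 points. At p=0.2 and p=0.35 it hardly moves. Average size changes more: 10.1 to 11.8 treated at p=0.5, against 8.44 stated.

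The conclusion in section 8.3, that stopping is unlikely below the 50% benchmark and likely well above it, survives. The replacement share is an assumption. The coverage gap and the two missing rows need none. With accrual closed, the consequence is for how the rule's properties are reported, not for protecting new patients.

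**What to change.** 1. Add two rows to Table 8: 8 of 12 (0.81) and 10 of 15 (0.85). Say that they follow the stated criterion of more than 0.8. The printed 5-of-7 row has 0.78 and does not meet it. If that row were taken as the standard, 9 of 14 (0.795) might be read as a boundary too, which would move the stopping probability at p=0.65 and 20% replacement only from 69.1% to 69.9%.
2. Re-run Table 9 for up to 15 patients, stating the replacement share assumed.
3. State in section 8.3 that every treated patient and every endpoint event counts, whether or not the patient is replaced.

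If no 11th patient was treated, one sentence saying so replaces items 1 and 2.

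The cost is two rows, one sentence and one simulation, with no extra patients. The downside is that the stated average number of subjects looks less favourable: at p=0.5, 10.1 with 20% replacement or 11.8 with all places used, instead of 8.44.

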### **5.11. Criteria for Early Trial Termination**

*Early trial termination will be the result of the criteria specified below:*

- Incidence or severity of adverse drug reaction in this or other studies indicates a potential health hazard to subjects. Please see section 8.0 Biostatistical Considerations for stopping rule calculations.

## **6.0 CLINICAL MONITORING**

### **6.1. Study Evaluations: Screening/Baseline**

**Screening:** Screening period will consist of the 28 days prior to C1 starting. During this time, patients will complete the necessary screening studies and testing. These will ordinarily be performed, prior to a patient signing consent for this protocol, on another screening Hematology Branch protocol (eg: 97-H-0041).

- Complete medical history
- ECOG performance evaluation

17-H-0026 (PD-AML)

[name], BM BCh DPhil

September 27, 2019

- Physical exam
  - Concomitant medication review
  - Complete blood count (CBC) with differential
  - Acute care & mineral panels (includes Na, K, Cl, CO2, creatinine, glucose, BUN, phosphorus, magnesium, albumin, and calcium)
  - Total protein, CK, Uric Acid, and LDH
  - Hepatic panel (includes alkaline phosphatase, ALT, AST, total bilirubin, and direct bilirubin)
  - Reticulocyte count
  - PT, PTT, fibrinogen
  - Thyroid function tests
  - Type and screen
  - Urinalysis
  - HLA typing
  - EKG
  - G6PD testing (as clinically indicated)
  - CMV IgG, IgM and PCR
  - Viral studies (serologies for HIV 1/2, hepatitis B and C). For individuals with a positive hepatitis B core antibody, HBV DNA PCR will be performed.
  - Peripheral blood flow cytometry (AML and T/B/NK).
- For females of childbearing potential, one negative pregnancy tests sensitive to 50 mIU within 72 hours prior to starting study drug.
- Baseline non-contrast computerized tomography scans of chest and sinus will be performed prior to, or in first five days after treatment initiation. Further baseline imaging will not be routinely performed except for those with a history of extra-medullary myeloid disease (also known as granulocytic sarcoma, myeloid sarcoma, or chloroma), another malignancy or disease where imaging represents the clinical standard of care, or suspicion for extra-medullary myeloid disease or ongoing infection.
- Baseline bone marrow aspiration and biopsy
    - Morphology and immunohistochemistry
    - Cytogenetics (karyotype) and/or FISH.
    - AML molecular testing panel (e.g.: c-Kit, FLT3-ITD, NPM1 or CEBPA mutation)
    - Flow cytometry

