#### 4.2. Exclusion Criteria

*The subject must be excluded from participating in the trial if the subject:*

- Has a diagnosis of acute promyelocytic leukemia (APL)
- Has previously received an allogeneic hematopoietic stem cell transplant.
- Has received AML treatment with an investigational therapy or device within 4 weeks of the first dose of treatment.
- Has a diagnosis of immunodeficiency or is receiving systemic steroid therapy or any other form of immunosuppressive therapy within 7 days prior to the first dose of trial treatment.
- Has a known history of active TB (Bacillus Tuberculosis)

- Has hypersensitivity to pembrolizumab or any of its excipients.
- Has hypersensitivity to decitabine or any of its excipients.
- Has received more than two prior cycles of decitabine.
- Has had a prior anti-cancer monoclonal antibody (mAb) within 4 weeks prior to study Day 1.
- Has had prior chemotherapy, targeted small molecule therapy, or radiation therapy within 2 weeks prior to study Day 1.

*Note: Subjects who have received cytoreductive therapy with hydroxyurea at any time prior to study Day 1 are an exception to this criterion.*

[figure not shown]
- Has not recovered (i.e.,  $\leq$  Grade 1 or at baseline) from adverse events due to previously administered AML therapy agents.
  - *Note: Subjects with  $\leq$  Grade 2 neuropathy are an exception and may qualify for the study.*
  - *Note: If subject received major surgery, they must have recovered adequately from the toxicity and/or complications from the intervention prior to starting therapy.*
- Has a known additional malignancy that is progressing or requires active treatment. Patients with basal cell carcinoma of the skin or squamous cell carcinoma of the skin that has undergone potentially curative therapy or in situ cervical cancer would not be excluded.
- Has known malignant central nervous system (CNS) involvement.
- Has active autoimmune disease that has required systemic treatment in the past 2 years (i.e. with use of disease modifying agents, corticosteroids or immunosuppressive drugs). Replacement therapy (eg., thyroxine, insulin, or physiologic corticosteroid replacement therapy for adrenal or pituitary insufficiency, etc.) is not considered a form of systemic treatment.
- Has history of (non-infectious) pneumonitis that required steroids, evidence of interstitial lung disease or active, non-infectious pneumonitis.
- Has an active infection requiring intravenous systemic therapy.

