## 5.0 TREATMENT PLAN

### 5.1. Treatment Schedule

Up to eight cycles of pembrolizumab will be given during the initial induction phase. Each cycle is 21 days. Decitabine will ordinarily be given on days 8 through 12 and 15 through 19 on alternative cycles (ie: cycles 1, 3, 5 and 7).

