### 5.3. Timing of Dose Administration

Pembrolizumab should be administered on Day 1 of each cycle after all procedures/assessments have been completed.

Pembrolizumab 200 mg will be administered as a 30 minute IV infusion every 3 weeks. Every effort should be made to target infusion timing to be as close to 30 minutes as possible. However, given the variability of infusion pumps, a window of -5 minutes and +10 minutes is permitted (i.e., infusion time is 30 minutes: -5 min/+10 min).

The Pharmacy Manual contains specific instructions for the preparation of the pembrolizumab infusion fluid and administration of infusion solution.

Decitabine will be administered at a dose of 20 mg/m^2 by intravenous infusion over approximately 1 hour repeated daily ordinarily on days 8 through 12 and 15 through 19 of alternative cycles (ie: cycles 1, 3, 5, 7). Decitabine may be given +/- 3 days, if needed for administrative or logistical issues. Decitabine should be repeated every 6 weeks. Patients may be premedicated with standard anti-emetic therapy. Every effort should be made to target infusion timing to be as close to 60 minutes as possible. However, given the variability of infusion pumps, a window of -5 minutes and +10 minutes is permitted (i.e., infusion time is 60 minutes: -5 min/+10 min).

These timings may change in accordance with section 5.2 above.

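### Section 6.1 lets the only routine chest CT follow the first pembrolizumab dose, so silent interstitial lung disease may be found after dosing and later lung events may lack a pre-treatment reference

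*Combined protocol and SAP*

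**What the plan says.** Section 6.1 defines screening by time: "Screening period will consist of the 28 days prior to C1 starting". In the same section the CT has its own, wider window: "Baseline non-contrast computerized tomography scans of chest and sinus will be performed prior to, or in first five days after treatment initiation". Other baseline imaging is reserved for stated circumstances, such as known or suspected extramedullary disease or suspected infection.

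Section 4.2 excludes a patient who "Has history of (non-infectious) pneumonitis that required steroids, evidence of interstitial lung disease or active, non-infectious pneumonitis", and separately one who "Has an active infection requiring intravenous systemic therapy".

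On the order of treatment, Section 5.3 says "Pembrolizumab should be administered on Day 1 of each cycle after all procedures/assessments have been completed", and Section 5.1 says "Decitabine will ordinarily be given on days 8 through 12 and 15 through 19 on alternative cycles". Appendix G, the schedule of clinical assessments, has no CT row. Section 11.2.4 describes CT as standard clinical care without a research use.

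**The concern.** A scan called a baseline would be expected to come before treatment. If it comes afterwards, two things are at stake.

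The first is eligibility. The lung-disease exclusion covers "evidence of interstitial lung disease or active, non-infectious pneumonitis". Disease without symptoms or a relevant history would not show on any other routine test in Section 6.1. A site could follow the plan exactly, give pembrolizumab, and then learn that the patient met an exclusion. The dose cannot be taken back: Section 2.3.2 reports a long half-life and target engagement lasting more than 21 days.

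The second is attribution of lung events. The primary outcome, feasibility, is a descriptive adverse event summary (Table 7). An infiltrate first seen on day 3 could be old or new. Calling it new overstates toxicity, and calling it old may hide an early reaction.

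**Working it through.** The plan gives no figure on this point to reproduce. The check is mainly of sequence, with a short calculation for scale.

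**1. Does the window reach past the first dose?**
- Table 4 and Section 5.3 put pembrolizumab on Day 1 of each cycle.
- Decitabine ordinarily starts on day 8 of cycle 1. With the 3-day allowance in Section 5.3, the earliest start is 8 − 3 = day 5.
- Treatment therefore begins with pembrolizumab, and a CT in the days after initiation follows it.

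**2. Does anything else bring chest imaging forward?**
- The pre-cycle assessments in Section 6.2 contain no imaging.
- Appendix G has no CT row.
- Section 11.2.6 mentions a chest x-ray, but only after central line placement, which is itself conditional.
- No other provision forces routine chest imaging before the first dose.

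**3. Which exclusions depend on the CT?**

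| Section 4.2 criterion | Can it be checked before dosing without the CT? |
|---|---|
| Past pneumonitis treated with steroids | Yes, from medical history |
| Active infection needing intravenous therapy | Yes, from history, examination and medication review; further imaging is available if infection is suspected |
| Interstitial lung disease or active non-infectious pneumonitis | Only if symptomatic or already known; silent disease needs imaging |

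**4. How do the event rules treat a finding on, say, day 3?**
- Section 9.1.1 starts the reporting period at the first dose, so the finding falls inside it.
- Section 5.2.2 accepts that immune events can appear soon after the first dose, so the finding could be a real early reaction.
- Section 9.6 requires listed events of clinical interest to be reported from the first dose whatever their attribution, and treats a possible immune-related event as immune-related when no other cause is found. Appendix C lists pneumonitis and interstitial lung disease from grade 2.
- Without a pre-dose scan, the evidence most useful for showing that a lesion was already there is missing.

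**5. Scale, using Section 11.2.1 (1562 subjects).**
- Any-grade pneumonitis: 45/1562 = 2.9%. The listed grades add up: 14 + 15 + 11 + 2 + 1 + 1 + 1 = 45.
- If that rate applied here (an assumption), the expected number in 10 patients is 10 × 0.0288 = 0.29, and the chance of at least one is 1 − (1 − 0.0288)^10 = 25%. At the maximum accrual of 15 these become 0.43 and 35%.
- Grade 4-5: (2 + 1)/1562 = 3/1562 = 0.19%. The chance of at least one in 10 is 1 − (1 − 3/1562)^10 = 1.9%, and in 15 it is 2.8%.
- Weight of one patient: 1/10 = 10 percentage points.

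**The case against.** The strongest reply is that no section names the CT as an eligibility test. Section 4.2 asks for evidence of lung disease without naming a method, and Section 11.2.4 gives the scan no research role. That is correct, and no Table 7 endpoint uses the CT. It does not remove the problem: the plan states an exclusion that silent disease can meet, and leaves the one routine test able to show it free to follow the dose.

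Four stronger readings are tempting and are not supported.

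- *The lung and infection exclusions can be checked only after treatment.* The table above shows otherwise for infection and for pneumonitis history. A scan taken before treatment, the first option in Section 6.1, also raises no issue.
- *Section 5.3 flatly contradicts Section 6.1.* The Section 5.3 wording, "after all procedures/assessments have been completed", is a general rule for every cycle, and the CT has its own specific window. This is a tension in wording. Absence from Appendix G is also weak evidence alone, since G6PD testing and the AML molecular panel have no row there either.
- *The stopping rule is compromised.* It counts grade 4 or 5 treatment-related events. The earliest boundary in Table 8 is 3 events in 3 patients, so one event alone cannot trigger it, and severe pneumonitis is rare at the background rate.
- *A specific, sizeable share of such trials would enrol a patient with an unseen lesion.* The documents give neither the prevalence of silent lung abnormality in this population nor the proportion scanned late, so no such probability can be calculated.

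Attribution is also not impossible. Table 10 allows for concurrent disease, and Sections 5.6 and 9.6 call for other causes to be ruled out. Those judgements are simply made with less information when the first scan is post-dose.

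**Conclusion.** The point holds in a limited form. Section 6.1 allows the only routine chest imaging to come after the first pembrolizumab dose. That leaves a gap in checking for silent interstitial lung disease or active pneumonitis, and weakens the reference for attributing later lung events. The size is modest: 10 percentage points per misclassified patient in a cohort of 10, with 0.29 pneumonitis cases expected if the monotherapy background rate carries over to this combination and population. The effect on the grade 4-5 stopping rule is negligible, at about a 2% chance of any such lung event in 10 patients under the same assumption. How many patients were in fact scanned after dosing is not known from the documents. This is an inexpensive improvement to the plan and does not invalidate the primary outcome.

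**What to change.** Reconcile Sections 4.2, 5.3 and 6.1 and Appendix G:

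- State that the planned chest and sinus CT supports the lung-disease check in Section 4.2.
- Delete the clause in Section 6.1 that allows the scan after treatment has begun, so that it falls within the 28-day screening period with the read available before cycle 1 day 1.
- Add the CT to the screening column of Appendix G.

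The cost is one sentence on purpose, one deleted clause and one table row. No scan is added, because every patient is already due to have one. The drawback is a possible short delay in starting treatment.

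Section 11.3 records that accrual closed on November 30, 2017 and that the study has been in data analysis only since March 15, 2019. The edit therefore serves a successor protocol. For this study, the report should list each patient's CT date relative to the first dose and flag any lung adverse event in a patient without a pre-dose scan. This needs only dates that should already be in the clinical record.
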